If a subject has a clinically significant, unresolved AE on Day 1 of C2 or beyond, the start of the cycle may be delayed for up to 14 days. Delays of >14 days must be approved by the medical monitor.

In the event a subject is unable to tolerate their dose level, additional treatment cycles (C2 or later) may be administered at a lower dose level upon approval by the medical monitor.

Table 14: Dose modifications for LV-associated toxicity (Part C [Arms 1 and 2]; 2q3wk dosing)

Toxicity	Grade 1	Grade 2	Grade 3	Grade 4
Peripheral neuropathy ^a	Continue at same dose level	Withhold until toxicity resolves to \leq Grade 1; then resume treatment at the next lower dose level (see Table 13)	Withhold until toxicity resolves to \leq Grade 1, then resume treatment at the next lower dose level (see Table 13)	Discontinue treatment
Hyperglycemia			Hold for blood glucose >250 mg/dL or >13.9 mmol/L. Resume treatment once elevated blood glucose has improved to ≤ 250 mg/dL or ≤ 13.9 mmol/L and subject is clinically and metabolically stable (see Section 5.6 for detail).	
Non-hematologic ^a (except peripheral neuropathy and hyperglycemia)	Continue at same dose level	Continue at same dose level	Withhold dose until toxicity is \leq Grade 2 or has returned to baseline, then resume treatment at same dose level ^b	Withhold dose until toxicity is \leq Grade 2 or has returned to baseline, then reduce dose to the next lower dose level (see Table 13) and resume treatment, or discontinue at the discretion of the investigator ^{b,c}
Hematologic ^a	Continue at same dose level	Continue at same dose level	Withhold until toxicity resolves to \leq Grade 2 or baseline ^{d,e} . For neutropenia, strongly consider G-CSF support , then resume treatment at the same dose level. Prophylactic G-CSF support should be strongly considered for subsequent cycles. (See Appendix G)	Withhold until toxicity resolves to \leq Grade 2 or baseline ^{d,e} . For neutropenia, strongly consider G-CSF support , then resume treatment at the same dose level. Prophylactic G-CSF support is required for all subsequent cycles. If Grade 4 neutropenia recurs despite G-CSF support, consider dose reduction to dose level -1 (see Table 13) or discontinuation. (Appendix G)

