Febrile neutropenia ^a			G-CSF support is required for treatment of febrile neutropenia. Withhold until febrile neutropenia resolves and neutrophil count returns to \leq Grade 2 or baseline then resume treatment at the same dose level. Prophylactic G-CSF is required for all subsequent cycles. If febrile neutropenia recurs despite G-CSF factor support, consider dose reduction to dose level -1 (see Table 13) or discontinuation.	

The maximum dose will be 200 mg per infusion for patients enrolled in Part C.

a Only 2 dose reductions are allowed without prior medical monitor approval. Additional toxicities should be managed with dose delays. Medical monitor approval is needed for further dose reduction.

b Subjects who develop Grade 3 or 4 electrolyte laboratory abnormalities may continue study treatment without interruption if a management plan consistent with institutional practice and regular monitoring are put in place.

c Treatment should be discontinued for subjects who experience Grade 4 infusion-related reactions.

d Support with blood product transfusions allowed per institutional standard of care.

e Subjects who develop Grade 3 or 4 lymphopenia may continue study treatment without interruption.

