5.4.1. Required Concomitant Therapy

G-CSF is required in the following situations.

- Part A: Subjects who experience Grade 4 neutropenia or febrile neutropenia (any grade) in any cycle with LV treatment must receive G-CSF treatment during the cycle, and must receive prophylactic G-CSF for all subsequent cycles.
- Part A: Subjects weighing over 80 kg and receiving >200 mg per infusion of LV in a cycle must be given prophylactic G-CSF, starting with their first dose of >200 mg per infusion. Once a subject receives G-CSF, it is strongly recommended that G-CSF continue to be administered to that subject at each subsequent cycle, regardless of weight change or LV dose, if it is deemed to be needed per investigator's clinical judgment.
- In Part B and Part C, primary prophylactic G-CSF is not required but is allowed (see Section [5.4.2 Allowed Concomitant Therapy](#) and Section [5.4.3. Myeloid Growth Factors](#)).

The administration of G-CSF should be consistent with American Society of Clinical Oncology (ASCO) guidelines ([Smith 2015](#)) ([Appendix G](#)).

- Prophylactic G-CSF should start 1 to 3 days after LV administration.
- G-CSF (including pegfilgrastim) should not be given within 24 hours prior to the dose of LV.
- If pegfilgrastim is used, a one-time dose per cycle is recommended.
- If daily G-CSF for treatment of AEs is used, treat for at least 5 to 7 days, or until the ANC is >1000/mm³ (\leq Grade 2).

If the subject is taking chronic suppressive or prophylactic anti-infectives (antiviral, antifungal, or antibacterial), documentation of investigations to ensure the absence of active infection must be completed prior to enrollment. The subject should continue suppressive or prophylactic anti-infectives for the duration of study participation.

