Strongly consider primary prophylaxis when allowed per protocol based on subject, disease, and treatment risk factors, including the following:

 • Age \geq65 years • Advanced disease • Previous chemotherapy or radiation therapy • Pre-existing neutropenia or bone marrow involvement with tumor • Infection • Open wounds or recent surgery 	
 • Poor performance status or poor nutritional status • Poor renal function • Liver dysfunction, most notably elevated bilirubin • Cardiovascular disease • Multiple comorbid conditions
---	---

In Part A: Secondary prophylaxis with G-CSF is required for all subsequent cycles for subjects who experience Grade 4 neutropenia or febrile neutropenia of any grade in any cycle while on LV (for which primary prophylaxis was not received), must receive G-CSF in all subsequent cycles. **G-CSF support is also required for treatment of febrile neutropenia.**

In Part B and Part C: Secondary prophylaxis with G-CSF is recommended for all subsequent cycles for subjects who experience a neutropenic complication with a previous cycle of therapy (for which primary prophylaxis was not received) when dose reduction or delay may compromise treatment outcome with LV. In Part B and Part C, primary prophylactic G-CSF is not required but is allowed.

In Part B and Part C: Treatment with G-CSF is strongly recommended for subjects with fever and neutropenia who are at high risk for infection-associated complications or who have prognostic factors that are predictive of poor clinical outcomes. High-risk features include:

 • Sepsis syndrome (hypotension and multi-organ dysfunction) • Age $>$65 years • Profound neutropenia (absolute neutrophil count $<$0.1 x 10⁹/L) • Neutropenia expected to last $>$7 days • Uncontrolled primary disease 	
 • Pneumonia • Invasive fungal infection • Other clinically documented infections • Hospitalization at time of fever • Prior episode of febrile neutropenia
--	--

As per ASCO guidelines, prophylactic G-CSF should start 1–3 days after LV administration. G-CSF (including pegfilgrastim) should not be given within 24 hours prior to the dose of LV. If pegfilgrastim is used, a one-time dose per cycle is recommended. If daily G-CSF is used, treat for least 5–7 days or until the ANC is $>$ 1000/mm³ (\leq Grade 2). Refer to the Prescribing

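### Part C Arms 1 and 2: Table 14 requires G-CSF after Grade 4 or febrile neutropenia, but Appendix G only recommends it and Section 5.4.1 leaves these arms off its required list

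*Protocol*

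**What the plan says.** Three places in the protocol deal with G-CSF after neutropenia in Part C Arms 1 and 2 (LV 1.5 mg/kg on Days 1 and 8).

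- **Section 5.2.4.3, Table 14.** For Grade 4 neutropenia, LV is withheld until recovery to Grade 2 or less, or baseline; G-CSF is to be strongly considered; and the site is to "then resume treatment at the same dose level. Prophylactic G-CSF support is required for all subsequent cycles". For febrile neutropenia the row opens with "G-CSF support is required for treatment of febrile neutropenia" and, after recovery, says "then resume treatment at the same dose level. Prophylactic G-CSF is required for all subsequent cycles". In both cases a dose reduction is to be considered only if the event recurs despite G-CSF.
- **Appendix G, Part B and Part C paragraphs.** "Secondary prophylaxis with G-CSF is recommended for all subsequent cycles for subjects who experience a neutropenic complication", with the condition that dose reduction or delay might compromise the outcome. For febrile neutropenia, "Treatment with G-CSF is strongly recommended for subjects with fever and neutropenia who are at high risk for infection-associated complications", or who have poor prognostic factors. For Part A the same appendix is mandatory: "Secondary prophylaxis with G-CSF is required for all subsequent cycles for subjects who experience Grade 4 neutropenia or febrile neutropenia of any grade".
- **Section 5.4.1, Required Concomitant Therapy.** The Part A entry says that subjects with Grade 4 or febrile neutropenia are to be treated with G-CSF in that cycle "and must receive prophylactic G-CSF for all subsequent cycles". The only entry for Part B and Part C is that "primary prophylactic G-CSF is not required but is allowed".

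**The concern.** Table 14 allows the full 1.5 mg/kg dose to be resumed after a serious neutropenic event and attaches a G-CSF mandate to that permission. The appendix it points to for G-CSF turns the mandate into a conditional recommendation, and the section headed as the list of required therapy does not mention it for these arms. The protocol does not say which text governs.

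A site that takes the dose from Table 14 and the G-CSF rule from Appendix G or Section 5.4.1 could give full-dose LV without prophylaxis and believe that it was compliant. A monitor could not settle from the text whether this was a deviation. What is at stake is subject safety and consistent conduct across sites.

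**Working it through.** No figure has to be reproduced; the check is a comparison of current text.

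| Situation, Arms 1 and 2 | Table 14 | Appendix G (Part C) | Section 5.4.1 |
|---|---|---|---|
| LV dose on resuming after a first event | Same level | Not stated | Not stated |
| Prophylaxis after Grade 4 neutropenia | Required, all later cycles | Recommended, with a condition | No entry |
| Prophylaxis after febrile neutropenia | Required, all later cycles | Recommended, with a condition | No entry |
| G-CSF to treat febrile neutropenia | Required | Strongly recommended if high risk or poor prognosis | No entry |
| G-CSF to treat Grade 4 neutropenia without fever | Strongly consider | No separate statement | No entry |

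1. **Is there a conflict?** Yes, between Table 14 and Appendix G, on secondary prophylaxis and on treatment of febrile neutropenia. Section 5.4.1 is silent for these arms. Its Part C sentence concerns primary prophylaxis only, so it omits the rule rather than denying it.
2. **Can one course of action satisfy all three?** Yes. A site that follows Table 14 also meets Appendix G and Section 5.4.1. The reverse fails: giving no prophylaxis can be consistent with Appendix G and Section 5.4.1 and still breach Table 14.
3. **Would a site plausibly reach the weaker rule?** Table 14's Grade 3 and Grade 4 hematologic cells cite Appendix G. Section 5.4.1 asks that G-CSF use follow the ASCO guideline and also cites Appendix G. The guideline text reproduced there says that dose reduction or delay may be a reasonable alternative to secondary prophylaxis, and that growth factors should not be routine alongside antibiotics in febrile neutropenia.
4. **Is Arm 3 affected?** No. Table 12 (Part B and Arm 3, weekly dosing) lowers the dose after Grade 4 or febrile neutropenia and carries no G-CSF mandate, which fits the Part B and Part C paragraphs of Appendix G. Those paragraphs suit the weekly arms and misfit the two 2q3wk arms.
5. **Scope.** Arms 1 and 2 plan 30 subjects each: 30 + 30 = 60 of the 90 in Part C.

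**The case against.** The best reply is that the texts can be read together. Appendix G is headed as recommendations and speaks to Parts B and C in general, while Table 14 is the specific instruction for the 2q3wk schedule. Same-dose resumption appears only in Table 14, so a site must read that instruction and overlook the next sentence of the same cell. The febrile neutropenia row does not cite Appendix G at all. Appendix G's high-risk features include uncontrolled primary disease, age over 65 and hospitalization at the time of fever, so many Cohort 8 subjects with fever would plausibly be covered by the strong recommendation anyway. LV is withheld until recovery, and Section 5.2.3.1 requires a neutrophil count of at least 1000/µL before the Day 1 and Day 8 doses.

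Most of this stands, and it limits the risk. It does not remove the contradiction: no text says that the specific table overrides the appendix, and the table itself sends the reader to the appendix. The Day 8 safeguard is also less firm later on, since Section 6.4.3.3 schedules a Day 8 blood count only in Cycles 1 and 2, whereas the prophylaxis rule covers all subsequent cycles.

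Two stronger readings are tempting but not supported:

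- A reader might infer that Table 12's dose reduction shows Table 14 to be the less protective rule. Per cycle, the reduced weekly dose is 3 × 1.0 = 3.0 mg/kg, equal to the unreduced 2q3wk dose of 2 × 1.5 = 3.0 mg/kg. Section 3.2.5 also explains that the free week was chosen partly to mitigate neutropenia.
- A reader might infer that Table 14 was carried over from Part A's Table 10 by mistake and that a reduction to 1.25 mg/kg was meant. The wording is close, but nothing in the protocol says this, and imposing a reduction would change treatment policy rather than correct an inconsistency.

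**Conclusion.** The inconsistency is real and lies in the current text. For 60 of the 90 planned Part C subjects, Table 14 makes G-CSF mandatory where Appendix G recommends it and Section 5.4.1 does not list it. The consequence is a possible resumption of 1.5 mg/kg without the prophylaxis that Table 14 attaches to it. The likelihood is limited by the placement of the mandate and by the neutrophil criterion.

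The 60 are the subjects whom the text covers, not an estimate of those harmed. The documents give no Grade 4 neutropenia rate and no neutropenia data on the 2q3wk schedule. A reader might borrow the figures for 1.5 mg/kg weekly in Section 3.2.5 (neutropenia in 67%, Grade 3 or higher in 44%). They do not transfer: they come from nine subjects, are not Grade 4 rates, and most of the clinically significant events followed three weekly doses, where 2q3wk gives two.

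The conclusion assumes that Table 14 states the sponsor's intention for these arms. No sample size, endpoint or analysis is affected. The correction should be made because it is cheap and concerns subject safety.

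**What to change.** - **Section 5.4.1:** add Part C Arms 1 and 2 to the required entry for Grade 4 and febrile neutropenia, in Table 14's terms: prophylaxis in all later cycles after either event, and G-CSF treatment for febrile neutropenia. The Part A entry should not be extended word for word, because it also requires G-CSF during the cycle for Grade 4 neutropenia, which Table 14 only asks the site to strongly consider.
- **Appendix G:** extend the mandatory Part A wording on secondary prophylaxis and on treatment of febrile neutropenia to Part C Arms 1 and 2. Limit the recommended and strongly recommended paragraphs to Part B and Part C Arm 3.
- **Precedence:** add one sentence saying that Table 14 governs G-CSF for Part C Arms 1 and 2.

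The cost is a few lines in a protocol amendment and a note to sites. Table 14, the LV dose levels and the timing limits on growth factors in Section 5.4.3 stay as they are.

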APPENDIX H. RECIST VERSION 1.1

Response Evaluation Criteria in Solid Tumors

Term	Definition
Complete response (CR)	Disappearance of all target lesions. Any pathological lymph nodes must have reduction in short axis to <10 mm.
Partial response (PR)	A $\geq 30\%$ decrease in the sum of diameters of target lesions, taking as reference the baseline sum diameters.
Progressive disease (PD)	At least a 20% increase in the sum of diameters of target lesions, taking as reference the smallest sum on study (this includes the baseline sum if that is the smallest on study). In addition to the relative increase of 20%, the sum must also demonstrate an absolute increase of at least 0.5 cm. The appearance of one or more new lesions is also considered progression.
Stable disease (SD)	Neither sufficient shrinkage to qualify for PR nor sufficient increase to qualify for PD, taking as reference the smallest sum diameters while on study.
Measurable lesion	Must be accurately measured in at least one dimension (longest diameter in the plane of measurement is to be recorded) with a minimum size of 10 mm by CT scan (CT slice thickness no greater than 5 mm).

From RECIST v1.1 ([Eisenhauer 2009](#))

APPENDIX I. IRECIST: GUIDELINES FOR RESPONSE CRITERIA FOR USE IN TRIALS TESTING IMMUNOTHERAPEUTICS

Response will also be assessed using iRECIST guidelines for determining eligibility of treatment continuation (Seymour 2017). Immunotherapeutics may result in infiltration of immune cells leading to transient increase in the size in malignant lesions, or undetectable lesions becoming detectable. The criteria are identical to those of RECIST Version 1.1 in many respects but have been adapted to account for instances where an increase in tumor burden, or the appearance of new lesions, does not reflect true tumor progression.

Key differences are described below. All responses defined using iRECIST guidelines are designated with a prefix; iRECIST time-point and best responses will be recorded separately.

Confirming Disease Progression

Unlike RECIST Version 1.1, the iRECIST guidelines require the confirmation of progression and use the terms iUPD (unconfirmed progression) and iCPD (confirmed progression). Confirmatory scans should be performed at least 4 weeks, but no longer than 8 weeks after iUPD.

For iCPD to be confirmed, further increase in tumor burden, compared to the last assessment, must be seen as evidenced by 1 or more of the following:

- Continued increase in tumor burden (from iUPD) where RECIST Version 1.1 definitions of progression had been met (from nadir) in target, non-target disease or new lesions
 - Progression in target disease worsens with an increase of at least 5 mm in the absolute value of the sum
 - Continued unequivocal progression in non-target disease with an increase in tumor burden
 - Increase in size of previously identified new lesion(s) (an increase of at least 5 mm in the absolute value of the sum of those considered to be target new lesions) or additional new lesions.
- RECIST Version 1.1 criteria are met in lesion types (target or non-target or new lesions) where progression was not previously identified, including the appearance of additional new lesions.

If iUPD is not confirmed at the next assessment, then the appropriate response will be assigned (iUPD if the criteria are still met, but no worsening, or iSD (stable disease), iPR (partial response), or iCR (confirmed response) if those criteria are met compared to baseline).

New Lesions

New lesions should be assessed and measured as they appear using RECIST Version 1.1 criteria (maximum of 5 lesions, no more than 2 per site, at least 10 mm in long axis [or 15 mm in short axis for nodal lesions], and recorded as New Lesions-Target [NLT] and New Lesion-Non-Target [NLNT]) to allow clear differentiation from baseline target and non-target lesions.

New lesions may either meet the criteria of NLT or NLNT to drive iUPD (or iCPD). However, the measurements of target lesions should NOT be included in the sum of measures of original target lesions identified at baseline.

APPENDIX J. PERFORMANCE STATUS SCALES CONVERSION
COPYRIGHTED MATERIAL

APPENDIX K. GUIDANCE ON CONTRACEPTION

For the purposes of this guidance, complete abstinence, if consistent with the subject's preferred lifestyle, is an acceptable form of contraception. Complete abstinence is defined as abstinence starting from the time of informed consent and continuing throughout the study and until the end of systemic exposure (at least 6 months after the final dose of study drug; see Section 4.1).

Acceptable methods for highly effective birth control (preventing conception)

Subjects who are of childbearing potential^a or whose partners are of childbearing potential^a and who are sexually active in a way that could lead to pregnancy may choose any TWO of the following methods:
• Hormonal methods of contraception (excluding progestin-only pills; method must be associated with inhibition of ovulation), unless contraindicated
• Intrauterine device with failure rate <1%
• Tubal ligation
• Vasectomy (at least 90 days from the date of surgery with a semen analysis documenting azoospermia)
• Barrier method/s (male or female condom with or without spermicide, cervical cap with or without spermicide, diaphragm with or without spermicide)

a A person of childbearing potential is defined as anyone born female who has experienced menarche and who has not undergone surgical sterilization (eg, hysterectomy, bilateral salpingectomy, bilateral oophorectomy) or has not completed menopause. Menopause is defined clinically as 12 months of amenorrhea in a person born female over age 45 in the absence of other biological, physiological, or pharmacological causes.

Acceptable methods for preventing secondary exposure to seminal fluid

Subjects born male and who are sexually active with a pregnant or breastfeeding person, must use the contraceptives in Option 1 or 2:
• Option 1: Male condom (with or without spermicide) and cervical cap
• Option 2: Male condom (with or without spermicide) and diaphragm

Unacceptable methods of contraception

- Periodic abstinence
- No method
- Withdrawal
- Rhythm
- Spermicide only
- Progestin-only pills
- Concomitant use of female and male condoms

APPENDIX L. PCWG3 SUGGESTED OUTCOME MEASURES FOR CLINICAL TRIALS IN METASTATIC PROSTATE CANCER

Variable	PCWG3 (2015)
Blood-based markers (PSA)	
 Recognize that a favorable effect on PSA may be delayed for ≥ 12 weeks, even for a cytotoxic drug Monitor PSA by cycle but plan to continue through early rises for a minimum of 12 weeks unless other evidence of progression Ignore early rises (before 12 weeks) in determining PSA response For control/relieve/eliminate endpoints: Record the percent change from baseline (rise or fall) at 8–9 or 12 weeks, depending on trial design, and separately, the maximal change (rise or fall) at any time using a waterfall plot Separately report the proportion of patients who have undergone radical prostatectomy and achieved a nadir less than 0.2 ng/mL; primary radiation therapy-treated patients who achieved a nadir less than 0.5 ng/mL Describe absolute changes in PSA over time from baseline to best response For delay/prevent end points (progression): After decline from baseline: record time from start of therapy to first PSA increase that is $\geq 25\%$ and ≥ 2 ng/mL above the nadir, and which is confirmed by a second value ≥ 3 weeks later (i.e., a confirmed rising trend); the requirement for an increase of 5 ng/mL was decreased to 2 ng/mL, and the requirement for a 50% increase was reduced to 25%. Recording the duration of PSA decline of little value No decline from baseline: PSA progression $\geq 25\%$ increase and ≥ 2 ng/mL increase from baseline beyond 12 weeks Relate to mechanism of drug and anticipated timing of potential favorable/unfavorable effects on PSA, if present
Imaging biomarkers: nodal and visceral For control/relieve/eliminate endpoints: General	
 Record changes in lymph nodes, lung, liver, adrenal, and CNS sites separately Record up to five lesions per site of disease Use RECIST v1.1 with caveats: 
 Record changes in size using waterfall plot Confirm favorable change with second scan Record complete elimination of disease at any site separately
Nodes	
 Only report changes in lymph nodes that were ≥ 1.5 cm in the short axis Record changes in pelvic (regional) nodes; extrapelvic (distant/metastatic) nodes separately

Visceral	
 Use RECIST v1.1 with caveats: Record changes in liver, lung, adrenal, and CNS separately Only report changes in lesions ≥ 1.0 cm in the longest dimension
For delay/prevent endpoints: Nodal and visceral	
General:
 
 Record changes in nodal and visceral (lung, liver, adrenal, and CNS) disease separately Use RECIST v1.1 but clearly record type of progression (growth of existing lesions; development of new lesions) separately by site The recommendations apply to both nmCRPC and mCRPC Record up to 5 lesions per site of spread Report the proportion who have not progressed at fixed time points (6 or 12 months) Note that for some treatments, a lesion may increase in size before it decreases
Nodal	
 Previously normal (<1.0 cm) lymph nodes must have grown by ≥ 5 mm in the short axis from baseline or nadir and be ≥ 1.0 cm in the short axis to be considered to have progressed Nodes that have progressed to 1.0 to less than 1.5 cm are pathologic, subject to clinical discretion, and nonmeasurable For existing pathologic adenopathy (≥ 1.5 cm), progression is defined per RECIST v1.1
Imaging biomarkers: bone Metastatic	
For control/relieve/eliminate end points:
 
 Record changes as improved or stable (no lesions), worse (new lesions), or resolved bone lesions Changes in intensity of uptake alone do not constitute progression or regression No new lesions: continue therapy in absence of other signs of progression New lesions (see Progression below) 
For delay/prevent end points (progression):
 
Progression:
 
 Exclude pseudo progression in the absence of symptoms or other signs of progression If at least 2 additional new lesions are seen on the next (confirmatory) scan, the date of progression is the date of the first post-treatment scan, when the first 2 lesions were documented For scans after the first post-treatment scan, at least 2 new lesions relative to the first post-treatment scan confirmed on a subsequent scan Date of progression is the date of the scan that first documents the second lesion

	
• Changes in intensity of uptake alone do not constitute either progression or regression• Report the proportion of patients who have not progressed at fixed time intervals (6 and 12 months)
--	---

mCRPC=metastatic castration-resistant prostate cancer; nmCRPC=nonmetastatic castration-resistant prostate cancer; PCWG3=Prostate Cancer Clinical Trials Working Group 3

Reference: ([Scher 2016](#))

